## 16. APPENDICES

### 16.1 National Early Warning (NEW) Score

([WHO Blueprint Master Protocol](#); [Royal College of Physicians 2012](#))

PHYSIOLOGICAL PARAMETERS	3	2	1	0	1	2	3
Respiration Rate (per minute)	≤8		9 - 11	12 - 20		21 - 24	≥25
Oxygen Saturations (%)	≤91	92 - 93	94 - 95	≥96			
Any Supplemental Oxygen		Yes		No			
Temperature (°C)	≤35.0		35.1 – 36.0	36.1 – 38.0	38.1 – 39.0	≥39.1	
Systolic BP (mmHg)	≤90	91 - 100	101 - 110	111 - 219			≥220
Heart Rate (per minute)	≤40		41 - 50	51 - 90	91 - 110	111 - 130	≥131
Level of Consciousness				A			V, P, or U

Level of consciousness = alert (A), and arousable only to voice (V) or pain (P), and unresponsive (U).

The aggregate results from all 7 physiological parameters are used to obtain the NEW Score.

**16.2 Extent of Dyspnea (Likert Scale)**

([Pang et al, 2014](#))

Subject ID: _____	Date: __/__/____	Clinician's Initials: ____
Time (24-hour clock): __h__		
Time Period:		
 baseline  Day 2  Day 4  Day 8  Day 14/15  Day 29		

Not completed

How is your shortness of breath **now** compared to when you **first started this study**?

Note: for your first questionnaire (at baseline), please compare your **current** shortness of breath to your shortness of breath **when you are well**.

Grade	Shortness of Breath	Please Choose One (mark with an 'X')
+3	Markedly Better	
+2	Moderately Better	
+1	Minimally Better	
0	No Change	
-1	Minimally Worse	
-2	Moderately Worse	
-3	Markedly Worse	

DO NOT PHOTOCOPY – ONLY USE ORIGINAL FOR SUBJECT COMPLETION  
Likert Dyspnea Scale Version 3.0\_3Apr2020

**16.3 Cough Severity Visual Analogue Scale**

([Birring and Spinou, 2015](#))

Protocol: AGN120-3

Subject #: \_\_\_\_\_

Clinicians initials: \_\_\_\_\_ Time (24-hour clock): \_\_h\_\_

Visit #: \_\_\_\_\_

Date: \_\_\_\_\_ / \_\_\_\_\_ / \_\_\_\_\_  
dd mmm yyyy

Not completed

**Cough Severity Visual Analogue Scale (VAS)**

How severe has your cough been over the last 24 hours?

Rate the severity of your cough by placing a single vertical line on the scale.

Date of Completion: \_\_\_\_\_(dd/mmm/yyyy)

Measurement: \_\_\_\_\_ mm (to be completed by study staff)

**DO NOT PHOTOCOPY – ONLY USE ORIGINAL FOR SUBJECT COMPLETION**  
Cough Severity Visual Analogue Scale (VAS) Version 2.0\_3Apr2020

1. INTRODUCTION

The following Statistical Analysis Plan (SAP) provides the outline for the statistical analysis of the data collected from the AGN120-3 study (protocol version 2.0 dated 16 November 2020). This SAP only covers the Phase2b part of the trial.

The planned analyses identified in this SAP may be included in clinical study reports (CSRs), regulatory submissions, or future manuscripts. Also, post hoc exploratory analyses not necessarily identified in this SAP may be performed to further examine study data. Any post hoc, or unplanned, exploratory analyses performed will be clearly identified as such in the final CSR.

2. PROJECT OVERVIEW

2.1 Study Design

This is a Phase 2b/3, multicenter, open label, randomized, parallel group study to evaluate the efficacy of Ifenprodil in patients with coronavirus disease of 2019 (COVID-19) disease.

In the Phase 2b phase, patients will be randomized in a ratio of 1:1:1 to either a) 20 mg TID IP plus Standard of Care group, b) 40 mg TID IP plus Standard of Care or c) Standard of Care only group. Investigators will collectively enroll approximately 50 evaluable patients in each treatment group, for a total of 150 patients. Patients receive either oral Ifenprodil (20 or 40 mg ter in die (TID)) for up to 14 days in addition to Standard of Care, or Standard of Care only. The Standard of Care (SOC) for each patient will be captured in the electronic clinical reporting form (eCRF).

Randomization will be stratified by site, and age (<65 versus ≥65).

For Phase 2b, one interim statistical analysis will be performed on selected efficacy endpoints and for safety for each arm after the first 75 patients have completed up to 2 weeks of treatment (Day 15). This analysis is being done to allow safety assessment and some snapshots of efficacy assessments as the trial progresses.

The Phase 2b study will also evaluate the different constructs of the ordinal scale (different days and different number of categories) by severity (severe vs. mild-moderate). Data from the Phase 2b study will be used to down select and prioritize the secondary endpoints. The protocol would then be amended for Phase 3 study to include the additional required number of patients to be recruited for the study to meet statistical significance in its primary endpoint.

An additional placebo arm will be added in the Phase 3 portion of the study. The number of participants to be enrolled in Phase 3 pivotal stage will be determined based upon the outcome of pilot Phase 2b stage of the study. Participants will be randomized to receive investigational product (IP) plus SOC, or Placebo plus SOC. Details will be outlined in a protocol amendment

Figure 1: Trial Design

[figure not shown]

Table 1 Schedule of Events

Trial Activity	Screening/Baseline/ Enrolment visit	Daily until hospital discharge	End of treatment	Follow-up period	
Day	1	2-14	15	29	60
Allowed window for visit (±)	-1 ^a		2	2	3
Visit	1		2 ^b	3	4
Informed consent	•				
Inclusion/exclusion criteria including confirmation of COVID-19 diagnosis	•				
Confirmation SARS-CoV- 2 ^h	•	•	•	•	
Pregnancy test	•				
Demographics/Medical History	•				
Physical Exam	•				
Vital signs ^c	•	•	•	•	
Clinical support data collection ^f	•	•	•	•	
Safety Laboratory Testing ^d	•	•	•	•	
Cytokine Markers ^k	•	•	•		
Child-Pugh Score ⁱ	•	•			
PaO2 and PaO2/FiO2 ratio ^j	•	•	•	•	
ECG	•				
Cough Severity (VAS) ^e	•	•	•	•	
Extent of Dyspnea (Likert Scale) ^e	•	•	•	•	
Adverse Events documented	•	•	•	•	•
Concomitant Medications	•	•	•	•	
Randomization	•				
Administer IP	•	•			
Vital Status					• ^g

^a Screening/baseline may occur up to 24 hours prior to randomization

^b Treatment can be given up to 14 days post randomization, or until hospital discharge, whichever comes first. If patient is discharged prior to Day 14, the next visit should be Visit 2.

^c Includes blood pressure (measured after the patient has been in a seated position (if possible) for ≥3 minutes of rest), pulse, respiratory rate, body temperature, and SpO2. Body weight and height will be measured at the screening visit only.

^d Baseline, Days 3, 5, 8, 11 if hospitalized, Day 15, Day 29

^e Baseline, Days 2, 4, 8, and 14 if hospitalized, Day 15 (if not done Day 14), Day 29

^f Includes NEW Score, on Baseline, Days 3, 5, 8, 11 if hospitalized, Day 15, Day 29

^g Vital status (is patient alive)

^h Baseline, Days 5 (or discharge, whichever comes first) and 15. Day 29 for patients with viral RNA detected at Day 15. Qualitative (mandatory) and Quantitative (if available) testing done all days.

ⁱ Baseline, Days 3, 5, 8, 11 if hospitalized

^j Minimum complete baseline, Days 3, 5, 8, 11, 15 and 29. If PaO2 not able to be taken, SpO2 should be obtained using a forehead sensor. Fingertip probes may be used if forehead sensors are not available. Remain consistent with the method of testing for the patient over the course of the study.

^k Cytokine markers at Baseline, Day 5, Day 15 (if available per local lab): IFN- γ , GM-CSF, IL-6, IL-12, TNF- α

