### 7.3.2 Daily Assessments (Days 2 - 14; Treatment Period)

At each study day while hospitalized, the following data will be collected:

- Vital signs (including pulse, respirations rate, body temperature, systolic and diastolic blood pressure, SpO2)
- Assess measures of clinical support
  - Hospitalized
  - Oxygen requirement
  - Non-invasive mechanical ventilation (via mask)
  - Mechanical ventilator requirement (via endotracheal tube or tracheostomy tube)
  - ECMO requirement
  - Ordinal Scale Assessment
  - The ordinal scale is an assessment of the clinical status at the first assessment of a given study day. Each day, the worse score for the previous day will be recorded. i.e. on Day 3, Day 2 score is obtained and recorded as Day 2. The scale is as follows:
    1. Not hospitalized, no limitations on activities
    2. Not hospitalized, limitation on activities
    3. Hospitalized, not requiring supplemental oxygen
    4. Hospitalized, requiring supplemental oxygen
    5. Hospitalized, on non-invasive ventilation or high flow oxygen devices
    6. Hospitalized, on invasive mechanical ventilation or ECMO
    7. Death
  - NEW Score (Days 3, 5, 8, 11 if still hospitalized)
- SARS-CoV-2 RNA status testing (Day 5, or discharge, whichever comes first)
- Safety laboratory testing (Days 3, 5, 8, 11 if still hospitalized)
- Child-Pugh Score (Days 3, 5, 8, 11 if still hospitalized)
- Cytokine Markers (Day 5)
- PaO2 and PaO2/FiO2 ratio
- VAS score questionnaire (Days 2, 4, 8, and 14 if still hospitalized)
- Extent of Dyspnea (Likert Scale, Days 2, 4, 8, and 14 if still hospitalized)
- Adverse Events recorded
- Concomitant medications
- IP administration (daily until discharge or Day 14)

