### 7.3.3 Visit 2 (Day 15 ±2; End of Treatment Period)

During this visit the following data will be collected:

- Vital signs (including pulse, respirations rate, body temperature, systolic and diastolic blood pressure, SpO2)
- Assess measures of clinical support
  - Hospitalized
  - Oxygen requirement
  - Non-invasive mechanical ventilation (via mask)

- Mechanical ventilator requirement (via endotracheal tube or tracheostomy tube)
- ECMO requirement
- Ordinal Scale Assessment
  1. Not hospitalized, no limitations on activities
  2. Not hospitalized, limitation on activities
  3. Hospitalized, not requiring supplemental oxygen
  4. Hospitalized, requiring supplemental oxygen
  5. Hospitalized, on non-invasive ventilation or high flow oxygen devices
  6. Hospitalized, on invasive mechanical ventilation or ECMO
  7. Death
- NEW Score
- SARS-CoV-2 RNA status testing
- Cytokine Markers
- Safety laboratory Testing
- PaO2 and PaO2/FiO2 ratio
- VAS (if not performed on Day 14; if possible)
- Extent of Dyspnea (if not performed on Day 14; if possible)
- Adverse Events recorded
- Concomitant medications

It is understood that restrictions on the return of study patients to the clinical site may be in place after their discharge from hospital. If not possible for the patient to return, the site may use remote methods (for example Telehealth, remote or nurse for hire, remote laboratories) to obtain the visit specific measurements/samples for both Visits 2 (Day 15; End of Treatment) and 3 (Day 29; Safety Follow Up Visit).

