2.3.3 Exploratory efficacy endpoints

- Changes in the extent of dyspnea from baseline, using a Likert scale, at Days 2, 4, 8, and 14 in IP versus control group
[Likert scale: The patient grades his/her current breathing compared to when he/she first started the study (from -3 to 3). "0" = no change, "1" = minimally better, "2" = moderately better, "3" = markedly better, "-1" = minimally worse, "-2" = moderately worse, "-3" = markedly worse]. For the first questionnaire (at baseline), the patient compares their current shortness of breath to their shortness of breath when they are well.
- Rate of change to patient's experience of cough (Visual analog scale [VAS]) at Days 2, 4, 8, and 14 in IP versus control group
VAS: The patient draws a vertical line on an axial graph (from 0 to 100) to show the degree of how he/she feels about coughing. The number "100" equals the worst coughing the patient has ever felt and the number "0" equals the best he/she has felt since baseline.
- Changes in D-dimer in IP versus control group
- Qualitative PCR for SARS-CoV-2 at baseline, days 5 (while hospitalized, and days 15 and 29 (if able to return to clinic or still hospitalized)
- Quantitative PCR (if available) for SARS-CoV-2 at baseline, days 5 (while hospitalized, and days 15 and 29 (if able to return to clinic or still hospitalized)

2.4 Safety Endpoints:

- Type, frequency, severity, and relationship of AEs to investigational product (IP)
- Number of patients who discontinue IP due to any AE
- Frequency of clinically significant changes in vital signs and/or laboratory findings

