11.10 Exploratory Analysis: Dyspnea

The Likert scale categories (0" = no change, "1" =minimally better, "2" =moderately better, "3" =markedly better, "-1" =minimally worse, "-2" =moderately worse, "-3" =markedly worse) will be reported using counts and percentages at all scheduled timepoints for all treatment arms and overall.

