11.11 Exploratory Analysis: Cough VAS and D-dimer

Percentage of change from baseline (defined in 3.2), change from baseline and actual values of Cough VAS and D-dimer at all scheduled timepoints will be summarized using continuous descriptive statistics (defined in 3.1) for all treatment arms and overall. T-test assuming unequal variance p-values and 95% CI comparing the differences between SOC and treatment arms A and B will also be provided for the percentage of change analysis.

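### Cough VAS on Day 14 and on Day 15 comes from near-complementary groups split by discharge, and SAP 11.11 tests each scheduled timepoint without a rule that combines them.

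*SAP*

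**What the plan says.** Footnote e to the schedule of events (SAP Table 1, repeated in protocol Table 3) sets the ratings at "Baseline, Days 2, 4, 8, and 14 if hospitalized, Day 15 (if not done Day 14), Day 29". The protocol's visit descriptions agree. Section 7.3.2 lists "VAS score questionnaire (Days 2, 4, 8, and 14 if still hospitalized", and section 7.3.3 lists "VAS (if not performed on Day 14; if possible" for Day 15. Footnote b covers earlier discharge: "If patient is discharged prior to Day 14, the next visit should be Visit 2".

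SAP 11.11 provides that "actual values of Cough VAS and D-dimer at all scheduled timepoints will be summarized using continuous descriptive statistics". It adds Welch t-test p-values and 95% confidence intervals for each ifenprodil arm against SOC on percentage change. SAP 3.1 presents summaries by arm and scheduled time point, and SAP 3.3 imputes nothing unless stated. No section says how a Day 14 and a Day 15 rating are to be combined.

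Dyspnea follows the same schedule (protocol 7.3.3: "Extent of Dyspnea (if not performed on Day 14; if possible"), but SAP 11.10 says only that the categories "will be reported using counts and percentages at all scheduled timepoints for all treatment arms and overall". No test is planned. The dyspnea form in protocol Appendix 16.2 has one box for Day 14 or 15. The cough form in Appendix 16.3 has a visit number and dates but no combined box. The endpoint list in SAP 2.3.3 names Day 14 and not Day 15 for both measures, for example "Changes in the extent of dyspnea from baseline, using a Likert scale, at Days 2, 4, 8, and 14".

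**The concern.** The schedule splits one end-of-treatment assessment into two parts according to whether the patient is still in hospital. The trial itself treats discharge as an efficacy outcome. If ifenprodil speeds discharge, the treated inpatients left on Day 14 are fewer and are no longer comparable with the SOC inpatients. The discharged groups are not comparable either.

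A t-test on either day then does not compare the groups as randomised. It can hide a real improvement in cough. It can also suggest harm where the drug speeds discharge and leaves cough unchanged. The named endpoint day, Day 14, is the smaller and more selected part. The ratings needed for a comparison of nearly all survivors are already scheduled, and the analysis text does not put them together.

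**Working it through.** **Inputs.** SAP 2.5 gives 50 patients per arm and the Table 2 Day 15 distribution at an odds ratio of 1.75. Table 2 is the only source in the documents for the share of patients in hospital around this time. Using it for Day 14 is an assumption.

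**Check of Table 2.** SOC categories 1 and 2 total 37 + 36 = 73%. The odds are 0.73/0.27 = 2.704. Multiplied by 1.75 they become 4.731, so the treated proportion is 4.731/5.731 = 82.6%. The printed treatment column gives 50.70 + 31.90 = 82.60%, so the table is reproduced. The Whitehead proportional-odds formula on this table gives a total of about 461, which is 462 in two equal arms, as stated. That sample size does not depend on this point.

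**Who contributes on each day** (every rating assumed to be obtained):

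| | SOC | Treated |
|---|---|---|
| In hospital (categories 3–6) | 17+5+2+1 = 25% | 11.45+3.03+1.2+0.6 = 16.28% |
| Day 14, of 50 | 12.5 | 8.1 |
| Discharged (categories 1–2) | 73% | 82.6% |
| Day 15, of 50 | 36.5 | 41.3 |
| Days combined, of 50 | 49.0 | 49.4 |

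In practice Day 15 also takes in any inpatient whose Day 14 rating was missed.

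**Size of the selection effect if cough equals severity.** Let severity be a standard logistic variable in SOC, shifted by ln 1.75 = 0.560 in the treated arm. Discharge lies below ln(0.73/0.27) = 0.995 and death above ln(0.98/0.02) = 3.892. A simulation with two million patients per arm gives these mean differences in latent units:

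- all survivors: 0.52
- Day 14 inpatients: 0.04 (0.04/0.52, about 8%)
- discharged patients: 0.32 (0.32/0.52, about 60%)

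**Weaker link between cough and severity** (assumed correlation 0.3 to 0.7, in SD of cough, negative meaning less cough on treatment):

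| Scenario | True effect | Day 14 | Day 15 | Combined |
|---|---|---|---|---|
| Cough improves through severity | −0.09 to −0.22 | −0.01 to −0.02 | −0.05 to −0.13 | −0.09 to −0.20 |
| Faster discharge, no effect on cough | 0 | +0.09 to +0.20 | +0.04 to +0.09 | about +0.01 |

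In both scenarios the combined timepoint lies close to the true effect and the separate days do not.

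**The case against.** **Separate tables are an inference.** SAP 11.11 refers to all scheduled timepoints, and the table layouts are in mock shells that are not part of these documents. The shells may already merge the days. This stands as a caveat. Separate days are nevertheless the natural reading of SAP 3.1 and 11.11, and one sentence in the SAP would settle it.

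**Dyspnea.** A reader might infer that both symptom comparisons are invalid in the same way. The documents do not support that. Dyspnea gets counts and percentages with no test or interval, and its form already treats Day 14/15 as one period. Only the wording of its timepoint needs alignment.

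**Precision.** From the counts alone, a reader might infer a Day 14 standard error about 2.2 times the combined one: √(1/12.5 + 1/8.14) / √(1/49 + 1/49.4) = 0.450/0.202. That assumes equal SDs. In the latent model the inpatient SD is about 0.72 against about 1.70 in survivors, so the standard errors are close: 0.323 on Day 14 and 0.343 combined. The problem shown here is bias, and no general loss of precision should be claimed.

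**Little rests on it.** Both endpoints are exploratory, and SAP 11.1 describes the pilot phase as exploratory. Protocol 10.9.2 plans only a descriptive summary of cough VAS. Day 29 ratings are scheduled whatever the hospital status. Even with cough equal to severity, the combined contrast has an expected z of only 0.52/0.343, about 1.5. All of this stands and keeps the point minor. It does not justify printing p-values for subsets selected by discharge.

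**Conclusion.** The point holds for cough VAS and is minor. Followed as written, SAP 11.11 yields Day 14 and Day 15 tests on near-complementary groups defined by discharge: about 12.5 against 8.1 patients and about 36.5 against 41.3. Neither test compares the randomised arms.

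The counts rest on Table 2 as a stand-in for status around Day 14 and on complete ratings. The latent differences of 0.52, 0.04 and 0.32 also assume that cough equals severity, which is an upper bound. They are in latent units, not the percentage change that the SAP tests. With weaker correlation the effects are smaller and the pattern is the same. No primary or secondary endpoint and no sample size is affected.

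**What to change.** - **SAP 11.11:** define one Day 14/15 analysis timepoint for cough VAS, taking the Day 14 value if present and otherwise the Visit 2 value. Run the by-arm summary and the t-test on it. Present Days 2, 4 and 8 as descriptive in-hospital data without p-values, because the same inpatient restriction applies there and combining Days 14 and 15 does not remove it.
- **SAP 11.10:** use the same combined timepoint for the dyspnea counts.
- **SAP 2.3.3 and protocol 3.2:** name the endpoint day as Day 14/15.
- **Protocol synopsis schedule:** reconcile it with Table 3. It lists the Day 15 VAS and dyspnea ratings without making them conditional on Day 14.

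The cost is SAP and protocol wording and one derived timepoint, with no new data. There are two drawbacks. With the Visit 2 window of ±2 days, a discharged patient may be rated as late as Day 17, about three days after an inpatient rated on Day 14, and possibly by remote methods. The comparison also remains one among survivors who have a rating, and the table should say so.

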2.2 Objectives

2.2.1 Primary objectives

To investigate the clinical efficacy and safety of NP-120 (20 and 40 mg TID) compared to standard of care in patients hospitalized with COVID-19 disease.

- The choice of the primary outcome measure will be determined by a pilot study of the first 150 patients.
- Patient clinical status (on the WHO 7-point ordinal scale) at day 15 is the default primary endpoint

2.2.2 Secondary objectives

To investigate the clinical efficacy of NP-120 (20 and 40 mg TID) as compared to the control arm as assessed by:

- **Ordinal scale:**
 - Time to an improvement of one category from baseline on an ordinal scale.
 - Patient clinical status on an ordinal scale at days 3, 5, 8, 11, and 29.
 - Mean change in the ranking on an ordinal scale from baseline to days 3, 5, 8, 11, 15 and 29 from baseline
- **National Early Warning Score (NEWS)**
 - The time to discharge or to a NEWS of ≤ 2 and maintained for 24 hours, whichever occurs first.
 - Change from baseline to days 3, 5, 8, 11, 15, and 29 in NEWS
- **Oxygenation:**
 - Oxygenation free days in the first 28 days (to day 29)
 - Effect on the rate of change of partial pressure of oxygen (PaO₂) and PaO₂/FiO₂ ratio taken at baseline and measured once daily up to 2 weeks of treatment in IP versus control group patients
- **Mechanical Ventilation:**
 - Ventilator free days in the first 28 days (to day 29)
 - Incidence and duration of new mechanical ventilation use during the trial
- **Hospitalization:**
 - Duration of hospitalization (days)
 - Time to discharge (days)
- **Mortality:**
 - 15-day mortality
 - 28-day mortality

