2.3.2 Secondary endpoints

- Status on an ordinal scale assessed daily while hospitalized and on days 15 and 28 in IP versus control group patients
- NEWS assessed days 3, 5, 8, 11 while hospitalized and on days 15 and 29 in IP versus control group patients
- Rate of mechanical ventilation in IP versus control group patients
- Duration of mechanical ventilation (if applicable) in IP versus control group patients
- Duration of supplemental oxygen in IP versus control group patients
- Time to return to SpO₂ > 94% on room air
- Duration in ICU (if applicable) in IP versus control group patients
- Rate of Mortality in IP versus control group patients
- Duration of hospitalization in IP versus control group patients
- Time to discharge in IP versus control group patients
- Effect on the rate of change of partial pressure of oxygen (PaO₂) and PaO₂/FiO₂ ratio taken at baseline and measured once daily up to 2 weeks of treatment in IP versus control group patients

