11.6 Secondary Efficacy Analysis: Respiratory Support

For the part of the analysis, respiratory support is defined as:

- Any respiratory support (any of Oxygenation only, Mechanical Ventilation (Invasive and non invasive), ECMO)
- Oxygenation only
- Invasive Mechanical Ventilation
- Non Invasive Mechanical Ventilation
- ECMO

11.6.1 Rate of Respiratory Support: Oxygenation only, Mechanical Ventilation (Invasive and non invasive), ECMO

Counts and percentages of patients for respiratory support at least once will be reported for each treatment arm. If patients were eligible for respiratory support but did not receive one due to lack of resources, an additional analysis on counts and percentages of patients required to receive respiratory support will be reported for each treatment arm. Separate 95% CIs (Newcombe) and p-values (Chi-Squared test without continuity correction) will be computed between SOC and treatment arms A and B for patients with at least one respiratory support.

11.6.2 Duration of Respiratory Support: Oxygenation only, Mechanical Ventilation (Invasive and non invasive), ECMO

Counts and percentages of patients with the following categories (based on total number of hours of respiratory support) will be reported for each type of respiratory support and for each treatment arm. The duration calculation is only applicable to patient with respiratory support. For patients with ongoing respiratory support with no end date and time at data cut off, the date of data cut off will be used to calculate the end date for the ongoing at time of data cut off category.

The duration is defined as:

Date and time at end of respiratory support-Date and time at end of respiratory support.

- < 6 hours
- \geq 6 hours but < 12 hours
- \geq 12 hours but < 24 hours
- \geq 24 hours but < 72 hours
- \geq 72 hours but < 120 hours
- > 120 hours
- Ongoing at time of data cut off (\geq 6 hours) [The hour can be amended based on real data]
- Ongoing at time of data cut off (\geq 12 hours) [The hour can be amended based on real data]
- Ongoing at time of data cut off (\geq XX hours) etc...
- Prolonged respiratory support (consecutive respiratory support for 21 days with at least \geq 6 hours per day)

Separate 95% CIs (Newcombe) and p-values (Chi-Squared test without continuity correction) will be computed between SOC and treatment arms A and B for prolonged respiratory support.

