11.8 Secondary Efficacy Analysis: Hospitalization and ICU

11.8.1 Duration of Hospitalization and ICU

Counts and percentages of patients with the following durations for hospitalization and ICU will be reported separately for each treatment arm. The duration calculation is only applicable to patient with the respective hospital or ICU stay. For patients with ongoing hospital or ICU stay with no end date at data cut off, the date of data cut off will be used to calculate the end date for the ongoing at time of data cut off category.

The duration for hospital/ICU stay (Day) is defined as:

Date at hospital discharge-Date of hospital admission+1.

Date at ICU discharge-Date of ICU admission+1.

- < 1 Day
- ≥ 1 Day but < 3 Days
- ≥ 3 Days but < 7 Days
- ≥ 7 Days but < 10 Days
- ≥ 7 Days but < 14 Days
- ≥ 10 Days but < 14 Days
- ≥ 14 Days but < 21 Days
- > 21 Days
- Ongoing at time of data cut off (≥ 1 Day) [The day can be amended based on real data]
- Ongoing at time of data cut off (≥ 3 Days) [The day can be amended based on real data]
- Ongoing at time of data cut off (≥ XX Days) etc...

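### Ventilator-free and oxygenation-free days are stated secondary objectives, but the SAP never defines or analyses them, and its duration analysis (11.6.2) has no rule for death

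*SAP*

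**What the plan says.** **Objectives.** SAP 2.2.2 lists "Ventilator free days in the first 28 days (to day 29") and "Oxygenation free days in the first 28 days (to day 29") as secondary objectives. The Protocol synopsis and Protocol 3.1 list the same two.

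**Endpoints.** SAP 2.3.2 and Protocol 3.2 do not carry them over. For ventilation they give a rate and "Duration of mechanical ventilation (if applicable) in IP versus control group patients"; for oxygen they give "Duration of supplemental oxygen in IP versus control group patients".

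**Analysis.** SAP 11.6.2 tabulates hours of support in bands and states that "The duration calculation is only applicable to patient with respiratory support". It has one special case: "For patients with ongoing respiratory support with no end date and time at data cut off, the date of data cut off will be used". Death is not mentioned. The bands are counts and percentages. The only between-arm comparison is a confidence interval and chi-squared test for prolonged support, meaning 21 consecutive days with at least 6 hours a day.

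**Elsewhere.** SAP 3.3 rules out imputation unless a section says otherwise. SAP section 13, on changes to the planned analysis, does not drop either objective.

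**The concern.** Two stated objectives would go unanswered if the plan were followed as written. Phase 2b is meant to help choose and rank the secondary endpoints for Phase 3 (Protocol 4.1, SAP 2.1), and a measure that is never computed cannot be judged for that purpose. The trial is open label. By SAP section 1, a definition added after the plan is final would have to be reported as post hoc.

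Free days combine survival and time off support in one value for every randomised patient. The duration table does neither. It drops patients who never had the support in question, and it does not separate coming off support alive from dying on it. For invasive ventilation the recipients are a group formed after randomisation. In the prolonged-support test, an early death on support takes the favourable value.

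**Working it through.** **1. Do the objectives have an analysis?** SAP section 11, read against them:

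| SAP section | What it gives | Why it does not replace free days |
|---|---|---|
| 11.6.1 | Rate of each support type by arm | Ever or never; no days, no deaths |
| 11.6.2 | Hours of support in recipients | No rule for death |
| 11.6.3 | Time to support, death as competing risk | Onset only; for oxygen probably not evaluable (step 2) |
| 11.6.4 | First oxygen to its first termination, death as competing risk | Oxygen only; later oxygen use ignored |
| 11.7.2 | Time to SpO2 above 94% on room air, death as competing risk | First attainment only |
| 11.8.2 | Time to hospital or ICU discharge, death as competing risk | Not a measure of support |
| 11.9 | Mortality | No support component |

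Ventilation has no counterpart to 11.6.4, so no analysis describes coming off the ventilator with death accounted for.

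**2. Oxygen in 11.6.3.** SAP 11.3 withholds a time-to-event analysis if any patient had the event before randomisation. Inclusion criterion 3 requires supplemental oxygen, non-invasive ventilation or high-flow oxygen at entry. Time to oxygen support is therefore probably blocked.

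**3. Death in 11.6.2.** As printed, the duration is "Date and time at end of respiratory support-Date and time at end of respiratory support", which is always zero. I read it as end minus start. With no rule for death, support that stops at death has an end time and gives a short duration. This is an inference from silence, but the SAP does state a death rule for the WHO scale (11.1), NEWS (11.5.1), 11.6.3, 11.6.4, 11.7.2 to 11.7.4 and 11.8.2.

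**4. Individual patients.** The documents give no definition of free days. I assume 28 minus days on the ventilator, and 0 if dead by Day 28.

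- Ventilated 2 days, then dies: 2 × 24 = 48 h, band 24 to under 72 h; free days 0.
- Ventilated 2 days, survives: 48 h, same band; free days 28 − 2 = 26.
- Ventilated 10 days, survives: 240 h, band over 120 h; free days 28 − 10 = 18.
- Never ventilated, survives: not in the table; free days 28.

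**5. Two constructed arms of 50, with 6 ventilated in each.** Deaths occur after 2 ventilated days, ventilated survivors have 10 days, and the other 44 patients are never ventilated and survive.

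- Arm X (1 death, 5 survivors): mean duration (48 + 5 × 240)/6 = 208 h; mean free days (0 + 5 × 18 + 44 × 28)/50 = 1322/50 = 26.4.
- Arm Y (5 deaths, 1 survivor): mean duration (5 × 48 + 240)/6 = 80 h; mean free days (0 + 18 + 44 × 28)/50 = 1250/50 = 25.0.

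Duration favours Y; free days favour X. Nobody reaches 21 days, so prolonged support is 0 of 6 in both arms. With death on support counted as unfavourable it is 1 of 50 against 5 of 50.

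**6. How many deaths might there be?** Table 2 assumes 2% mortality at Day 15 under standard of care. Per arm of 50 that is 50 × 0.02 = 1 expected death, and the chance of at least one is 1 − 0.98^50 = 0.64. Over an assumed range of 1% to 15%, expected deaths are 0.5 to 7.5. These are all deaths, not only deaths on support.

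**The case against.** The strongest reply is that the plan already covers respiratory support well, with death handled in most places. That is largely right, and it limits the point.

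- A reader might infer that the SAP studies support solely through durations in recipients. It does not: 11.6.1 compares rates, 11.6.3 keeps non-recipients as censored, and 11.6.4, 11.7.2 and 11.8.2 treat death as a competing risk. The early-death artefact is addressed for the end of oxygen support and for discharge.
- A reader might infer that duration was put in place of free days. Duration of ventilation and of oxygen are endpoints in their own right. The fault is that the free-day objectives were not carried forward.
- A reader might take all of 11.6.2 as a biased treatment comparison. Its bands are descriptive; only the prolonged-support test compares arms.
- Selection after randomisation matters mainly for invasive ventilation and ECMO, because every eligible patient already has some form of oxygen support at entry.
- A reader might add categories 6 and 7 of Table 2 to estimate the ventilated share. That is Day 15 status, it counts the dead as ventilated, and the documents give no ever-ventilated rate.

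It is also fair that Phase 2b is exploratory, that about one death per arm would distort little, and that ventilator-free days would be heavily tied if few patients are ventilated. What remains is that two objectives have no analysis, ventilation has no analysis of coming off support, and one planned test gives early death the favourable value.

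**Conclusion.** The point holds in this form. Both 28-day measures are stated objectives with no endpoint entry, definition or analysis; this rests on the text alone. That 11.6.2 reads death on support as a short or non-prolonged duration is an inference from its silence, together with the no-imputation rule. The constructed arms show that the direction can reverse; they do not estimate an effect in this trial. The size depends on deaths on support, which the documents do not give. On Table 2's planning figure it would be small, and it grows with mortality. The change should be made before the SAP is final, but the primary analysis is not affected.

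**What to change.** 1. Add both measures to SAP 2.3.2 and to 11.6 and 11.7. State the start of the 28-day window, which types of support count (11.6 separates oxygen only, invasive ventilation, non-invasive ventilation and ECMO), a value of 0 for death by Day 28, and a rule for days after discharge.
2. Analyse them in all ITT patients, each ifenprodil arm against SOC, with the age- and site-adjusted proportional-odds model of 11.1.
3. In 11.6.2, compute the prolonged-support comparison in all ITT patients with death on support before 21 days counted as unfavourable, or make it descriptive. Correct the printed duration formula at the same time.

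Setting death to 0 is one choice among several. If the sponsor does not want these measures, the objectives should be removed openly by amendment.

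**Cost.** Two extra tables. SAP 11.6.2 already presupposes dated start and end of support, and vital status is collected at Day 60. There are two drawbacks. Values will be heavily tied if few patients are ventilated. After discharge, oxygen need is scheduled for recording only around Days 15 and 29, so the days between need a stated assumption.
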